4.3 Sample and Data Collection for Immune Sub-Study

Maternal blood samples will be collected pre- and post-vaccination. We anticipate study visits occurring 4 weeks up to vaccination, four weeks after vaccination, and again twelve weeks after vaccination. Maternal blood samples will also be collected at delivery. We anticipate these study visits to occur +/- 2 days at delivery, and 4-6 weeks after delivery. If the delivery sample is within the window of another collection time point, we will collect only one sample. SARS-CoV-2 serology will be performed for all maternal samples to determine IgG seropositivity rate and semi-quantitative antibody levels to anti-spike protein. IgG class sub-typing will be performed on maternal samples. Additionally, serology for IgG and IgA antibodies will be performed on selected maternal blood samples. Cord blood samples at delivery and infant blood samples at 4-6 weeks post-delivery will be collected and analyzed on serologic assays and compared to peripartum maternal antibody levels.

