4.2 Data Collection

Once consent has been obtained, the baseline survey will automatically be pushed to the participant. The baseline answers will determine if pregnancy and or vaccine outcome surveys are to be answered at the same time. A short follow-up questionnaire will be administered on December 1st 2023 and another on February 1st 2024 to capture changes in vaccination status, COVID-19 status, pregnancy outcomes or significant health events. The follow-up surveys will determine if/when outcome surveys need to be completed. If consent is withdrawn, the study will immediately cease for the participant. The survey modules are as follows:

1. Baseline survey: Pregnancy status, vaccination status, demographics, health history, COVID-19 history & pregnancy history - Administered at enrollment starting Sept 1, 2023 until Jan 31, 2024

2. Pregnancy Outcomes: Pregnancy & infant outcomes – Administered if pregnancy started in 2023 and are not currently pregnant

3. Vaccine Outcomes: Answered if a dose of a COVID-19 vaccine received during the current pregnancy

4. Vaccine Attitudes 1: Feelings, opinions & attitudes towards vaccines– Administered at end of surveys received at baseline

5. Vaccine Attitudes 2: Feelings, opinions, and attitudes towards the Respiratory syncytial virus (RSV) – Administered following the completion of Vaccine Attitudes 1

6. Follow-up survey: 2 time-based follow-up surveys administered on December 1st, 2023, and on February 1st, 2024 with reminders sent out periodically throughout study duration
7. Health Event: Significant health events resulting in a visit to the emergency department or hospitalization – Administered if triggered by Follow-up survey

In the event of an adverse reaction or major health event, the study team will contact a participant for further health information.

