4.5 Statistical Analysis and Metrics

To adequately power for comparisons of adverse events, we used estimates of vaccine-related adverse events (i.e. pain at injection site, redness, swelling, fever, fatigue, chills, headache, muscle pain, joint pain, grade 4 serious adverse events) from the subset of younger participants in the Pfizer vaccine trial, as an example (12). The rate of overall adverse events was 25%, and with a sample size of 451 in the vaccinated cohort we could estimate this prevalence with $\pm 4\%$ precision and 95% confidence. Sample sizes are highly feasible and will allow for comparison of adverse obstetrical and infant outcomes between vaccinated and unvaccinated participants. Given a sample size of 500 per group (vaccinated vs. unvaccinated) we would have 80% power to detect a minimum relative risk of 1.5.

The immunogenicity sub-study would require 89 participants, assuming 10% loss to follow up to estimate a 70% seroconversion rate with \pm 10% precision and 95% confidence. A seroconversion rate closer to 80% would require 68 participants. For comparisons of antibody levels, using estimates for the 18-55y age group (13) we would need approximately 48 participants to demonstrate a 10% difference in geometric mean titer with 95% power and assuming an attrition rate of 10% per visit.

The presence of any adverse outcomes (vaccine and pregnancy-related) will be compared between vaccinated and unvaccinated using time-varying Cox's proportional hazards models (14), stratified by vaccine type, and including important confounders. Effectiveness will be assessed descriptively through participant reporting of positive SARS-CoV-2 tests and COVID-19 diagnoses in vaccinated

and unvaccinated participants. Clinical features of breakthrough cases will be described in those vaccinated. Exploratory analyses will investigate differences between vaccinated and unvaccinated people. Clinical severity will be compared with unvaccinated people in the CANCOVID-Preg cohort. This will include tracking of infections with variants of concern where possible in both vaccinated and unvaccinated participants.

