4.6 Statistical Analysis for the Immune Sub-Study

Seroconversion will be estimated and compared to licensure data using binomial tests. Antibody levels in pregnancy will be compared to licensure data for the relevant vaccine and dose using one-sample t-tests. We will stratify by gestational age, participant age, and other co-factors that might influence immune response. Maternal antibody levels will be compared to infant levels at birth, controlling for infant gestational age at delivery, birth weight, and infant feeding. Exploratory analysis of antibodies in breast milk will be compared to maternal serum antibody levels.

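### Anti-spike is the only antigen named and COVID-19 is last asked about on 1 February 2024, so infection before later blood draws cannot be separated from vaccine response

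*Protocol*

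**What the plan says.** **Assay.** Section 4.3: "SARS-CoV-2 serology will be performed for all maternal samples to determine IgG seropositivity rate and semi-quantitative antibody levels to anti-spike protein". It adds IgG sub-typing and says that "serology for IgG and IgA antibodies will be performed on selected maternal blood samples". These additions describe antibody class; no second antigen and no laboratory marker of infection is named.

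**Draws.** Section 4.3 places maternal visits at "4 weeks up to vaccination, four weeks after vaccination, and again twelve weeks after vaccination", with further maternal samples at delivery and 4-6 weeks after it. Cord blood is taken at delivery and infant blood at 4-6 weeks.

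**Infection data.** The baseline survey takes COVID-19 history; Section 4.2 gives its timing as "Administered at enrollment starting Sept 1, 2023 until Jan 31, 2024". After that, short surveys on 1 December 2023 and 1 February 2024 are meant "to capture changes in vaccination status, COVID-19 status, pregnancy outcomes or significant health events". The health-event module is triggered by those surveys.

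**Analysis.** Section 4.6: "Antibody levels in pregnancy will be compared to licensure data for the relevant vaccine and dose using one-sample t-tests". It also compares maternal with infant levels at birth, and stratifies by gestational age, participant age and unnamed co-factors that might influence immune response. For the antibody comparison, Section 4.5 plans "approximately 48 participants to demonstrate a 10% difference in geometric mean titer with 95% power and assuming an attrition rate of 10% per visit". The same section expects breakthrough cases and will describe them.

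**The concern.** A participant infected between her dose and a later draw carries anti-spike antibody from both sources, and the named assay cannot apportion it. Section 1.3 offers the sub-study only to people who intend to be vaccinated in pregnancy, and Section 4.6 compares them with external licensure data. No concurrent unvaccinated group is therefore sampled that could show how much antibody infection adds.

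Known infections can be handled in the analysis. Infections that nobody asked about cannot, and the survey dates leave a stretch in which nobody is scheduled to ask. The resulting error runs upward: it can produce an apparent excess over licensure levels or offset a true shortfall. It does not shrink with sample size. Immunogenicity is listed among the primary objectives in Section 2.0, and a 10% target is small enough for a few infected participants to matter.

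**Working it through.** **1. The plan's own figures.** The 48 for the titre comparison cannot be reproduced, because the SD of log titre is not given. The neighbouring seroconversion figures do reproduce from n = 1.96² × π(1−π)/0.10²:
- π = 0.70 gives 80.7, and × 1.1 gives 88.7 (stated: 89).
- π = 0.80 gives 61.5, and × 1.1 gives 67.6 (stated: 68).

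**2. Which draws fall after the last infection question.**
- 12 weeks is 84 days, and 1 February 2024 minus 84 days is 9 November 2023. Every dose after that date has its 12-week draw after the last survey date. Baseline enrolment runs to 31 January 2024 and the first sub-study draw precedes the dose, so such doses are expected.
- Eligibility (Section 3.2) is pregnancy beginning in 2023. Assuming 38 weeks (266 days) from conception to term delivery, conceptions after about mid-May 2023 deliver after 1 February 2024. Their delivery, cord and 4-6-week samples come later still.
- The Summary gives a timeline ending in March 2024. If sampling also stopped then, the uncovered stretch would be at most about eight weeks. The protocol does not say that it does.

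**3. Size of the bias in titre.** Let p be the share of participants infected between dose and draw, and k the fold rise that infection adds. The mean log titre rises by p × ln k, so the geometric mean is multiplied by k^p. A 10% rise needs p = ln 1.10 / ln k = 0.0953 / ln k.

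| k (assumed) | p for +10% | people in 48 |
|---|---|---|
| 1.5 | 23.5% | 11.3 |
| 2 | 13.8% | 6.6 |
| 4 | 6.9% | 3.3 |
| 10 | 4.1% | 2.0 |

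Inflation at assumed p and k:

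| p | k = 2 | k = 4 | k = 10 |
|---|---|---|---|
| 2% | +1.4% | +2.8% | +4.7% |
| 5% | +3.5% | +7.2% | +12.2% |
| 10% | +7.2% | +14.9% | +25.9% |

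**4. Effect on the one-sample test.** Assume two-sided 5% and one visit of attrition: 48 × 0.9 = 43.2 evaluable. Solving the stated 48 backwards gives an SD of ln titre of 0.0953 × √43.2 / (1.960 + 1.645) = 0.174. With no true difference, shift p × ln k and variance 0.174² + p(1−p)(ln k)², a normal approximation rejects in:
- 16.7% (p = 5%, k = 2)
- 25.7% (p = 5%, k = 4)
- 39.0% (p = 10%, k = 2)
- 52.5% (p = 10%, k = 4)

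The nominal rate is 5%. These figures depend on the SD solved from 48 and are illustrative only.

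**5. Effect on seroconversion.** If every infected non-responder seroconverts, p = 10% moves 70% to 0.70 + 0.30 × 0.10 = 73%, and 80% to 0.80 + 0.20 × 0.10 = 82%. Both shifts lie well inside the planned ±10% precision.

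**The case against.** The strongest reply is that the protocol does not say what it might be read as saying. A reader might infer that the sub-study keeps samples taken after infection and counts them as vaccine response. The text says only that all maternal samples are tested; a rule for excluding or flagging results is ordinary SAP content, and the SAP is not at hand. Known infections are collected at baseline and in two surveys, Section 4.2 foresees contact after a major health event, and the co-factor wording in Section 4.6 is broad enough to include infection. All of this stands, and it confines the point to infections that are not recorded.

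Three further limits also stand. Section 4.6 compares levels in pregnancy with licensure data, not every sample; cord, infant and post-delivery levels enter only other comparisons, and the direction of any bias in the maternal-infant relation is not shown. No waning or durability analysis is stated, so a claim that waning is hidden goes beyond the text. Section 4.5 does not say which draw the 10% refers to; at the 4-week draw, exposure is short and p correspondingly smaller.

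What the reply does not meet is the calendar. An SAP can act only on infections the study has recorded. Reminders relate to the existing surveys, so a late-completed February form may catch some later infections, but by accident and not by schedule.

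**Conclusion.** The point holds in a limited form. With anti-spike the only antigen and the last scheduled infection question on 1 February 2024, infection before later draws is not systematically recorded and cannot be told apart from vaccine response. That is a data-collection gap which analysis cannot repair.

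The size is conditional. The inflation reaches the 10% target at 13.8% infected with a 2-fold rise, 6.9% with 4-fold or 4.1% with 10-fold. It stays at +7.2% for 5% infected with 4-fold, or 10% with 2-fold. The stronger reading, that infection will exceed the target difference, is not supported: the protocol supplies neither an infection rate nor a fold rise. Seroconversion is little affected. The matter concerns the titre comparison and, in an undetermined direction, the maternal-infant comparison. It merits a change because the remedy is cheap and must be in place before the samples are taken.

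**What to change.** **Section 4.3:** at every blood draw, including delivery and 4-6 weeks after delivery, ask about SARS-CoV-2 infection or a positive test since the last contact, with its date.

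**Section 4.6:** report the titre and maternal-infant comparisons twice, with all samples and without samples taken after a reported post-dose infection. As a sensitivity analysis, flag a rise in anti-spike after the 4-week sample without a new dose (for example at least two-fold) as possible unreported infection.

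**Cost:** one question per existing visit, and slightly wider intervals in the analysis with exclusions. Excluding infected participants conditions on an event after the dose: if weaker responders are infected more often, exclusion itself raises the geometric mean. That is why both analyses are needed. The change is partial, since unreported infection before the 4-week sample, or infection whose rise is offset by waning, is still missed.

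### The one-sample t-test of semi-quantitative antibody levels against licensure data cannot separate a difference in assay scale from an effect of pregnancy unless both sides are in the same unit

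*Protocol*

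**What the plan says.** Three places in the protocol bear on this.

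- **Section 4.3** describes the readout: "SARS-CoV-2 serology will be performed for all maternal samples to determine IgG seropositivity rate and semi-quantitative antibody levels to anti-spike protein". It names no assay, unit, calibrator or reporting range.
- **Section 4.6** fixes the analysis: "Antibody levels in pregnancy will be compared to licensure data for the relevant vaccine and dose using one-sample t-tests". It attaches no condition on unit or post-dose time point, and mentions neither a log scale nor a bridging step.
- **Section 4.5** sizes antibody comparisons: "we would need approximately 48 participants to demonstrate a 10% difference in geometric mean titer with 95% power", with variability taken from a cited external study and "assuming an attrition rate of 10% per visit". It prints no SD.

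The sub-study (section 1.3) enrols people who intend to be vaccinated during pregnancy. The protocol describes no non-pregnant group whose samples would be run on the same assay.

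**The concern.** A one-sample t-test compares a sample mean with a number taken as known and as measured on the same scale. Here that number comes from outside the study. If the study's readings differ from the licensure scale by a constant factor, the log mean shifts by the log of that factor, exactly as it would under a true pregnancy effect of that size. Nothing in the test tells the two apart. A larger sample does not help, because it makes rejection for the wrong reason more likely.

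A significant result would naturally be read as a weaker or stronger antibody response in pregnancy. Immunogenicity is among the primary objectives (section 2.0), and section 4.7 plans monthly reports to public health partners and the public, so a misattributed difference could travel quickly.

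**Working it through.** **The protocol's own figure.** The 48 participants in section 4.5 can be neither confirmed nor refuted, because no SD is printed. It can only be inverted. For a one-sample t-test on the log scale with a ratio of 1.10, 95% power and two-sided 0.05 (alpha and sidedness are not stated for this test):

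- 48 evaluable requires an SD of 0.179 on the natural-log scale (0.078 log10), a geometric SD of exp(0.179) = 1.20.
- 28 evaluable requires 0.135 (0.059 log10), a geometric SD of exp(0.135) = 1.14.

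The 28 comes from applying 10% attrition at each of the five maternal collection times in section 4.3: 48 × 0.9^5 = 28.3. The protocol does not say how many visits it counted.

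**Effect of a scale gap when pregnancy has no effect.** Inputs:

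- Evaluable n: 48 (section 4.5), and 28 as above.
- Two-sided alpha 0.05: assumed.
- Geometric SD (GSD) 2 to 3: assumed.
- Constant scale factor k between the study assay and the licensure scale: assumed at 1.1, 1.25, 1.5 and 2. No value of k can be taken from the protocol.

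Formula: on log levels, the t statistic is noncentral t with n − 1 degrees of freedom and noncentrality ln(k) × √n / ln(GSD). The rejection probability is the area beyond the critical value, 2.012 for n = 48 and 2.052 for n = 28.

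Worked cases for k = 1.5, ln(1.5) = 0.4055:

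- n = 48, GSD 2: 0.4055 × 6.928 / 0.6931 = 4.05, rejection 98%.
- n = 48, GSD 3: 0.4055 × 6.928 / 1.0986 = 2.56, rejection 71%.
- n = 28, GSD 2: 0.4055 × 5.292 / 0.6931 = 3.10, rejection 85%.
- n = 28, GSD 3: 0.4055 × 5.292 / 1.0986 = 1.95, rejection 47%.

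Probability of a significant result with no true pregnancy effect (nominal 5%), GSD 3 to GSD 2:

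| Scale gap k | 48 evaluable | 28 evaluable |
|---|---|---|
| 1.1 | 9-15% | 7-11% |
| 1.25 | 28-59% | 18-38% |
| 1.5 | 71-98% | 47-85% |
| 2 | 99% or more | 90-99.9% |

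**Sensitivity to the SD.** The assumed GSD of 2 to 3 is much wider than the 1.20 that the 48 would imply for a one-sample test. With an SD as small as that, a 1.1-fold gap alone would be declared significant 95% of the time at n = 48, since it is by construction the effect the test is powered to find. The assumed range therefore does not exaggerate the problem relative to the protocol's own sizing, if that sizing applies to this test.

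**The case against.** **Laboratory detail belongs elsewhere.** Assay, calibrator and unit are commonly left to a laboratory manual or SAP, and the SAP is not at hand. Matching on vaccine and dose shows that some comparability is intended. This stands as far as the missing unit goes, and the absence alone would not be a finding. It does not dispose of the point, because section 4.6 itself fixes the test and the comparator and makes the comparison unconditional.

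**No gap is shown to exist.** This stands. The protocol describes neither its own assay nor those behind the licensure data. A reader might infer that the scales do differ, or that the bias would run in opposite directions for different vaccines. The document supports neither.

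**The 10% difference is not tied to this test.** This stands. Section 4.5 attaches "to demonstrate a 10% difference in geometric mean titer" to comparisons of antibody levels in general, and attrition counted per visit fits a repeated-visit comparison at least as well. A reader might infer that a 10% scale gap would consume the whole effect the licensure test seeks. The document does not say so, and at GSD 2 to 3 a 10% gap raises rejection only to 9-15%.

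**The rates are illustrative and fall with smaller n.** This stands. Testing by vaccine and dose could leave fewer per test than even the 28 shown.

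**The immunogenicity objective does not hang on this one test.** This stands. Seroconversion estimates, gestational-age strata and maternal-infant comparisons are also planned. Reading the point as meaning that the whole objective would give a wrong answer goes too far.

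**Conclusion.** The point holds in a limited form. Run as section 4.6 is written, the one-sample t-test cannot attribute a significant difference to pregnancy, because nothing in the stated design excludes a scale difference between the study's semi-quantitative readings and the licensure values. That is a property of the test and needs no assumption about how large a gap there is.

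The size of the consequence does depend on assumptions: the gap, the geometric SD and the number evaluable. For gaps of 1.5-fold, rejection with no true effect is far above the nominal 5% throughout the range tried. For a gap near 10% the inflation is modest unless the SD is as small as the protocol's 48 would require.

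The binomial seroconversion comparison and the maternal-infant comparison lie outside this conclusion. The change is worth making before analysis.

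**What to change.** In section 4.6, state that antibody levels are analysed on the log scale, and that the one-sample t-test against a licensure value is done only where that value is in the same calibrated unit and at a comparable post-dose time point. Where either condition fails, drop the test and show the licensure value descriptively at most. In that case, base the antibody-level conclusion on contrasts run on one assay from samples section 4.3 already collects: pre-vaccination against 4 and 12 weeks, gestational-age strata, and maternal against cord blood. Section 4.3 should name the reporting unit or point to the document that does.

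The cost is wording, plus a unit conversion where a valid one exists; no new samples are needed. The downside is that the external comparison is lost for any vaccine without a licensure value in the same unit. The same-assay contrasts describe response within pregnancy and do not replace a comparison with non-pregnant people.

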4.4 Data Management / Stewardship

Participants will enter survey data directly into a secure REDCap database housed at the national coordinating centre at the University of British Columbia (UBC). The REDCap software uses a web server designed to enable secure transfer of data between a client computer and the data centre, located in a highly-secured area at the BC Children's Hospital Research Institute. Support for data management will be provided by the Faculty of Medicine Digital Solutions Research Technology Unit.

4.5 Statistical Analysis and Metrics

To adequately power for comparisons of adverse events, we used estimates of vaccine-related adverse events (i.e. pain at injection site, redness, swelling, fever, fatigue, chills, headache, muscle pain, joint pain, grade 4 serious adverse events) from the subset of younger participants in the Pfizer vaccine trial, as an example (12). The rate of overall adverse events was 25%, and with a sample size of 451 in the vaccinated cohort we could estimate this prevalence with $\pm 4\%$ precision and 95% confidence. Sample sizes are highly feasible and will allow for comparison of adverse obstetrical and infant outcomes between vaccinated and unvaccinated participants. Given a sample size of 500 per group (vaccinated vs. unvaccinated) we would have 80% power to detect a minimum relative risk of 1.5.

The immunogenicity sub-study would require 89 participants, assuming 10% loss to follow up to estimate a 70% seroconversion rate with \pm 10% precision and 95% confidence. A seroconversion rate closer to 80% would require 68 participants. For comparisons of antibody levels, using estimates for the 18-55y age group (13) we would need approximately 48 participants to demonstrate a 10% difference in geometric mean titer with 95% power and assuming an attrition rate of 10% per visit.

The presence of any adverse outcomes (vaccine and pregnancy-related) will be compared between vaccinated and unvaccinated using time-varying Cox's proportional hazards models (14), stratified by vaccine type, and including important confounders. Effectiveness will be assessed descriptively through participant reporting of positive SARS-CoV-2 tests and COVID-19 diagnoses in vaccinated

and unvaccinated participants. Clinical features of breakthrough cases will be described in those vaccinated. Exploratory analyses will investigate differences between vaccinated and unvaccinated people. Clinical severity will be compared with unvaccinated people in the CANCOVID-Preg cohort. This will include tracking of infections with variants of concern where possible in both vaccinated and unvaccinated participants.

Vaccine confidence and attitudes, including intention to receive the COVID-19 vaccine, will be assessed using a validated survey grounded in the Theory of Planned Behaviour (TPB)(15) and part of the WHO Vaccine Hesitancy Scale (VHS)(16). The TPB is well established as a psychological model to predict and understand health-related behaviours. This theory defines the most significant predictors of a health behaviour as attitudes, social norms (direct, indirect), and perceived behavioural controls; measures of each of these predictors will be included in the survey. Prior evidence from Canada has shown that this model is able to accurately predict vaccine uptake (17,18). The factors included in the VHS are vaccine lack of confidence and vaccine risk. All items in the TPB and VHS are measured on a 5-point Likert scale. Vaccine attitudes will be reported overall and by vaccination status. Comparisons among subgroups (e.g. by age, region, cultural background, and gender) will be conducted using linear regressions. Importantly, comparisons among subgroups (e.g. by age, region, cultural background, and gender) will identify priority areas for vaccine education and outreach.

As gender does not exist in isolation from other socially-relevant contextual factors such as class, immigrant status, rurality, race, and indigeneity which, in turn, also affect health outcomes. We will collect data on all these factors and our analysis will adopt a SGBA+ approach to compare vaccine attitudes between gender groups and how these interact with other intersectional variables.

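### The 451 said to power adverse-event comparisons is a one-group precision size, and the listed vaccine reactions cannot support the planned comparison with the unvaccinated

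*Protocol*

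**What the plan says.** Protocol Section 4.5 opens the sample-size paragraph with its purpose: "To adequately power for comparisons of adverse events". The events meant are vaccine reactions: "pain at injection site, redness, swelling, fever, fatigue, chills, headache, muscle pain, joint pain, grade 4 serious adverse events". The rate is taken from a vaccine trial ("The rate of overall adverse events was 25" per cent). The calculation then reads "with a sample size of 451 in the vaccinated cohort we could estimate this prevalence" to within ±4%, with 95% confidence.

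The same paragraph goes on to say that the sample sizes will allow obstetrical and infant outcomes to be compared between vaccinated and unvaccinated participants. It adds that 500 per group gives 80% power for a minimum relative risk of 1.5. That sentence gives no baseline risk and no significance level.

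Later in Section 4.5, any adverse outcome, vaccine-related as well as pregnancy-related, is to be compared between vaccinated and unvaccinated in a time-varying Cox model stratified by vaccine type. Section 4.2 restricts the Vaccine Outcomes module: "Answered if a dose of a COVID-19 vaccine received during the current pregnancy". The follow-up surveys go to all participants and can trigger the Health Event module, which covers emergency visits and hospitalization. Section 2.0 lists the impact of co-administration as objective 5.

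**The concern.** The protocol claims power for comparisons and supports the claim with a calculation that compares nothing. A precision size answers how well one rate is known. It does not say what difference between two groups would be found.

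The comparator is also a problem. The 25% is a rate of vaccine reactions. Unvaccinated people cannot have pain, redness or swelling at the site of a COVID-19 injection, and the protocol describes no reaction module for them. A vaccinated-versus-unvaccinated hazard ratio for such events is settled by how they are defined and collected, so it tells nothing about safety.

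Section 4.7 promises monthly reports to public health partners and the public. Readers could take a reported comparison of reactions, or the absence of a difference between vaccine types or with co-administration, as something the study was sized to test.

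**Working it through.** **1. The protocol's own figure.** Inputs, all from Section 4.5: p = 0.25, half-width d = 0.04, 95% confidence (z = 1.96), one group.

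n = z² p(1 − p) / d² = 1.96² × 0.25 × 0.75 / 0.04² = 450.2, rounded up to 451.

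The figure reproduces exactly. At n = 451 the half-width is 1.96 × √(0.25 × 0.75 / 451) = 0.03996, or 4.0 points. The formula contains no second group, no alternative and no power, so 451 is a correct precision size and nothing more.

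**2. Whether the 500 per group fills the gap.** As pure arithmetic, 500 per group with 25% against 37.5% (RR 1.5) gives 99% power (pooled two-proportion test, two-sided 5%). That needs a comparator in which the event can occur and is recorded. Set against Sections 4.2 and 4.5:

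- Injection-site pain, redness and swelling (3 of the 10 listed events) cannot occur in the unvaccinated.
- Fever, fatigue, chills, headache, muscle pain and joint pain can occur in anyone. The only module described for vaccine outcomes, however, is confined to those vaccinated in the current pregnancy. I take this module to be where reactions are recorded, since the protocol does not list its items.
- Serious events leading to an emergency visit or hospitalization reach both groups through the follow-up and Health Event surveys.
- Pregnancy and infant outcomes are collected whatever the vaccination status.

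Only the last two classes give a usable contrast with the unvaccinated.

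**3. What 451 would give within the vaccinated.** The protocol gives no significance level and no split by vaccine type or co-administration, so both are assumed here. With reference rate p1 = 0.25 in the larger subgroup, two-sided 5% and pooled rate p̄ weighted by subgroup size:

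power = Φ{ [ (p2 − p1) − 1.96 √( p̄(1 − p̄)(1/n1 + 1/n2) ) ] / √( p1(1 − p1)/n1 + p2(1 − p2)/n2 ) }

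For an even split and p2 = 0.375: p̄ = 0.3125, the null term is 1.96 × 0.04365 = 0.0856, and the denominator is 0.0433. Power = Φ[(0.125 − 0.0856) / 0.0433] = Φ(0.91) = 82%.

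| Split of 451 (assumed) | Detectable at 80% power | Difference | RR | Power for RR 1.5 | Power for 10 points |
|---|---|---|---|---|---|
| 50:50 | 25% vs 37.2% | 12.2 points | 1.49 | 82% | 64% |
| 70:30 | 25% vs 38.2% | 13.2 points | 1.53 | 76% | 58% |
| 80:20 | 25% vs 40.1% | 15.1 points | 1.60 | 65% | 48% |
| 90:10 | 25% vs 45.2% | 20.2 points | 1.81 | 45% | 32% |

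With 500 vaccinated instead of 451, the detectable RRs are 1.46, 1.50, 1.57 and 1.76. The ±4 points does not carry over to a difference either. With both rates near 25%, the 95% half-width for an even split is 1.96 × √(0.1875 × 2/225.5) = 0.080, or 8 points, and it is about 10 points at 80:20.

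**The case against.** The strongest reply is that one introductory clause is loose and the next sentence puts it right. The protocol says that 451 estimates a prevalence, the arithmetic is sound, and a power statement with a second group and an alternative follows in the same paragraph. On this reading the opening clause covers the whole paragraph, precision first and power second. Part of this stands: there is no arithmetic error, and the protocol does state power for a comparison. It does not rescue the claim about adverse events. The events named after the opening clause are vaccine reactions, whereas the power statement is introduced for obstetrical and infant outcomes and has no usable comparator for those reactions.

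A second reply is that no test between products or by co-administration is specified. Stratifying by vaccine type qualifies the Cox model, and objective 5 names no hypothesis test. This stands. A statistical analysis plan could settle such contrasts, so their missing power is a caution and not a contradiction.

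A reader might infer that comparisons within the vaccinated are weak. The documents do not support that without conditions. An even split of 451 gives 82% power for RR 1.5, which meets the protocol's own benchmark, and with 500 vaccinated a 70:30 split also reaches RR 1.50 at 80% power. The shortfall against RR 1.5 depends on unequal splits, and the protocol gives no split.

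A reader might also infer that none of the ten events can be compared with the unvaccinated. That goes too far. Systemic symptoms can occur in both groups and are limited only by how they are collected, and serious events are captured in both.

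**Conclusion.** The point holds in a limited form. The 451 is a one-group precision size presented as powering comparisons. The 500-per-group statement does not supply power for the listed reactions, and the planned Cox comparison of vaccine-related outcomes with the unvaccinated has no meaning for injection-site events. For other reactions recorded only in the vaccinated, it has no data to work on.

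The first part rests on the protocol's own formula inputs and needs no assumption. The second rests on reading the Vaccine Outcomes module as the place where reactions are collected; for injection-site events it holds regardless. The sizes for contrasts within the vaccinated (80% power from about 12 points upward, RR 1.49 to 1.81) rest on a 25% reference rate, two-sided 5% and assumed splits. They show what 451 would deliver and do not show that a planned test fails. No sample size has to change, and the point is minor.

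**What to change.** 1. In Section 4.5, state that 451 vaccinated participants estimate a 25% adverse-event prevalence within ±4 points at 95% confidence, call this a precision target, and drop the claim that it powers comparisons.
2. Restrict the vaccinated-versus-unvaccinated Cox comparison to events that can occur in, and are collected from, both groups: pregnancy and infant outcomes, and health events leading to an emergency visit or hospitalization. Report vaccine reactions descriptively in the vaccinated with 95% intervals.
3. If reactions are contrasted within the vaccinated, by vaccine type or co-administration, state that 451 was not sized for this, and give the detectable difference with its assumed split, reference rate and significance level.

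The cost is wording and a narrower comparison. The property the protocol can claim becomes less favourable; recruitment and data collection are unaffected.
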